3.2.1.2 Secondary efficacy analysis

All secondary and exploratory analyses will be performed using thesstr2 positive evaluable population only.

Similar to the primary endpoint, the selection of the optimal PET imaging time of ^{68}Ga -OPS202 will be based on the provided outputs for all secondary and exploratory efficacy endpoints.

Key Secondary Endpoint:

a) Absolute number of lesions detected by ^{68}Ga -OPS202 in nodular and metastatic lesions

For each PET/CT assessment, the individual number of lesions detected by ^{68}Ga -OPS202 in nodular and metastatic lesions (result from both readers as well as final result) will be listed by subject and by PET acquisition timepoint. If there is a high number of lesions (≥ 35 lesions) in any one organ, identifying and counting of the lesions is not feasible as it cannot be accurately done. The absolute number of lesions will be presented as a category “ ≥ 35 lesions” if such case occurs.

Values will be available in the database provided by ICL.

A listing of all discrepancies between both readers in the nodular and metastatic lesions will also be presented by subject and PET acquisition timepoint.

Image quality

For each PET/CT assessment, each independent blinded reader will perform a direct comparison of the three ^{68}Ga -OPS202 scans acquired at different times (0.5, 1 and 2 hours) in nodular and metastatic lesions.

Individual values of quality score for nodular and metastatic lesions and reason for selecting scan will be listed per reader, by subject and by PET acquisition timepoint

b) Lesion SUV_{max} and tumour-to-background ratio

Lesion SUV_{max}

For each PET assessment, the SUV_{max} (unit-less measure) will be measured for each lesion, up to a maximum of the five most avid lesions per organ identified by one of the primary readers.

In order to obtain a unique measure per organ, the mean of the SUV_{max} will be computed within each of the six following organs:

- Primary breast lesion
- Liver
- Lymph nodes
- Bone
- Lungs
- Brain.

Values will be available in the database provided by ICL.

Tumour-to-background ratio

For each PET assessment, the tumour-to-background ratio will also be measured for each lesion, up to a maximum of the five most avid lesions per organ, as follow:

Tumour to background ratio

$$= \frac{\textit{Lesion SUVmean}}{\textit{SUVmean of the subject's reference tissue (tumour free liver *)}}$$

*If insufficient tumour free liver is available for reference tissue, then aortic blood pool will be used as background.

The tumour-to-background ratio will be obtained using the mean of all lesions tumour-to-background ratios for each of the six following organs:

- Primary breast lesion
- Liver
- Lymph nodes
- Bone
- Lungs
- Brain.

Tumour-to-background ratio is a unit-less measure where a high tumour-to-background ratio indicates high effectiveness of $^{68}\text{Ga-OPS202}$ as a diagnostic agent, in a similar manner to SUV_{max} .

Individual values of the lesion SUV_{max} , lesion SUV_{mean} , SUV_{mean} of the subject's reference tissue and tumour-to-background ratio will be listed by subject, by each of the six organs and by PET acquisition timepoint.

Other Secondary Endpoints:

c) Relative lesion count

The relative lesion count is the ratio of the number of lesions detected by $^{68}\text{Ga-OPS202}$ at each of the three PET acquisition timepoints compared to the number of lesions assessed by standard-of-truth ($^{18}\text{F-FDG-PET}$ scan).

For each PET/CT assessment, this ratio will be computed as indicated below:

$$\text{Relative lesion count} = \frac{\text{Number of lesions detected by } ^{68}\text{Ga} - \text{OPS202}}{\text{Number of lesions detected by } ^{18}\text{F} - \text{FDG} - \text{PET}}$$

Relative lesion count will be computed over all lesions of all organs and for each of the following organs:

- Primary breast tumour (among all subjects with at least one lesion detected by ^{18}F -FDG-PET in primary breast tumour).
- Lymph nodes (among all subjects with at least one lesion detected by ^{18}F -FDG-PET in lymph nodes).
- Liver (among all assessed subjects with at least one lesion detected by ^{18}F -FDG-PET in liver).
- Axial/appendicular skeleton (bone) (among all assessed subjects with at least one lesion detected by ^{18}F -FDG-PET in bone).
- Lungs (among all assessed subjects with at least one lesion detected by ^{18}F -FDG-PET in lungs)
- Brain (among all assessed subjects with at least one lesion detected by ^{18}F -FDG-PET in brain).

For the per organ analysis, the relative lesion count will be:

- Equal to 0 if there is no lesion identified in the specific organ on ^{68}Ga -OPS202 scan.
- Missing if the numerator is missing (for example in case of non-readable ^{68}Ga -OPS202 PET scan at timepoint) with non-null denominator
- Not analyzed if there is no lesion identified in the specific organ on ^{18}F -FDG-PET scan.

If there are 35 lesions or more counted on both ^{68}Ga -OPS202 and ^{18}F -FDG-PET scans, then the relative lesion count will be set to 100%. If any of the two scans has a count of ≥ 35 , the relative lesion count will be computed using a count of 35 lesions for the scan showing more than 35 lesions.

Individual values of the relative lesion count will be listed by subject, by organ and by PET acquisition timepoint.

d) Absolute number of lesions detected by ^{68}Ga -OPS202 in lymph nodes, liver, Axial/appendicular skeleton, lungs and brain

For each PET/CT assessment, the number of lesions detected by ^{68}Ga -OPS202 will be reported for each of the five following anatomic sites:

- Lymph nodes
- Liver
- Axial/appendicular skeleton (Bones)
- Lungs
- Brain

Values will be available in the database provided by ICL.

Individual values of the number of lesions detected by ^{68}Ga -OPS202 (results from both readers and final result) will be listed by subject, organ and PET acquisition timepoint.

- e) The second component of the co-primary and appropriate secondary endpoints will also be evaluated on a radioactivity dose/kg of body weight.

This analysis will not be provided.

Exploratory efficacy endpoints:

- f) Preliminary diagnostic sensitivity of ^{68}Ga -OPS202 imaging of breast cancer expressing sstr2 positive by both subject-based and lesion-based analysis compared to standard-of-truth

This analysis will not be provided.

g) SUV_{max} ratio for lesions

This analysis will not be provided.

h) SNR

For the primary breast lesions, the SNR will be computed as follows:

$$SNR = \frac{SUV_{mean}}{SUV_{SD} \text{ of the subject's reference tissue (tumour - free liver *)}}$$

*If insufficient tumour free liver is available for reference tissue, then aortic blood pool will be used instead.

Values will be available in the database provided by ICL.

A higher SNR indicates higher effectiveness of ⁶⁸Ga-OPS202 as a diagnostic agent.

Individual values of SNR will be listed by subject and by PET acquisition timepoint.

i) Estimated correlation in terms of number of avid lesions between ⁶⁸Ga-OPS202 PET at the agreed "optimum timepoint" and ¹⁸F-FDG-PET

This analysis will not be provided.

j) Estimated correlation between ⁶⁸Ga-OPS202 PET uptake and results of immunohistochemistry staining of sstr2 of the primary tumour.

This analysis will not be provided.

3.2.2 *Safety*

All safety data will be provided in both data listings and summary tables and using the Safety population.

3.2.2.1 *Adverse events*

All AEs will be recorded and graded by investigators using the NCI CTCAE classification (Version 5.0), will be coded using the MedDRA Version 20.1 or higher, and will be classified by MedDRA PT and SOC.

Listings will be presented and sorted by subject number, start date of AEs, primary system organ class, preferred term and verbatim text for all adverse events recorded during the study.

Listings of SAEs, AEs leading to IIP withdrawal and AEs leading to death (fatal outcome) will also be presented. Also, a listing of grade ≥ 3 AEs will be provided.

Treatment Emergent Adverse Events (TEAEs) will be flagged (*) in the AE listings and will be summarised.

A TEAE is defined as any AE that occurs during the study if:

- (1) it was not present prior to receiving the ^{68}Ga -OPS202 injection, or
- (2) it was present prior to receiving the ^{68}Ga -OPS202 injection but the grade increased during the study, or
- (3) it was present prior to receiving the ^{68}Ga -OPS202 injection, the grade is the same but the causality changed to “related” during the study.

■ [REDACTED] CCI [REDACTED]

An overall summary table of all AEs will be presented.

In that table, in the cross classification of causality and intensity, any subject experiencing multiple AEs with different intensities for each causality category will be counted for each grade.

3.2.2.2 *Laboratory data*

A separate listing of normal ranges for Standard International (SI) units will be provided by age where relevant.

Laboratory data (serum haematology and biochemistry panels, urinalysis) will be listed in SI units and abnormal values will be flagged (high [H], low [L], clinically significant [C], NCI-CTC grade (G)) where applicable. Any unscheduled laboratory assessments will be flagged [U] in the listings.

Subject listings will be presented by subject number and visit.

- **Haematology and Biochemistry**

For haematology and biochemistry parameters, the baseline will be defined as the last measurement collected prior to IIP administration (Visit 2 Day 1).

Shift tables for haematology and biochemistry parameters will be presented of the number and percentage of subjects with low, normal or high values.

Haematological and biochemistry toxicities will be recorded and graded according to the NCI-CTC criteria, Version 5.0. The NCI-CTC grade 3 and 4 haematology and biochemistry parameters by subject and by visit will be listed. Listings of the laboratory parameters in appendix 2 section 14.3.4 will include listings of NCI-CTC Grade 3 and 4 haematological toxicities, listings of NCI-CTC Grade 3 and 4 biochemical toxicities and listings of out of range biochemistry parameters that could not be graded using NCI-CTC grade (below Lower Limit of Normal range (LLN) – normal – above Upper Limit of Normal range (ULN)).

- **Urinalysis**

For categorical urinalysis data (absent/trace/positive of protein, ketones, bilirubin, blood, urobilinogen, nitrites, leukocyte esterase and glucose), frequency tables will be presented at each scheduled assessment (Baseline, post-dose, EOS/EW).

3.2.2.3 *Vital signs*

Vital signs (body temperature, supine and standing blood pressure and heart rate, respiratory rate), body weight and BMI will be listed at each assessment by subject. Any unscheduled vital signs will be flagged [U] in the listing.

Baseline values will be defined as the last vital signs measurement collected prior to IIP administration.

Summary statistics will be presented at each scheduled assessment for actual values and changes from baseline.

Following assessments will be summarised for body temperature, blood pressure, heart rate and respiratory rate: Baseline, 0.5h Post-dose, 1h Post-dose, 2h Post-dose, 4h Post-dose, Visit 2 Day 2, EOS/EW.

Weight and BMI will be analysed at Baseline, Visit 2 Day 2 and EOS/EW.

3.2.2.4 *ECG*

ECG results will be listed at each assessment (Screening, EOS/EW) by subject. Any unscheduled ECG will be flagged [U] in the listings.

Baseline will be defined as the last ECG measurement collected prior to IIP administration.

For continuous ECG parameters (RR duration, PR duration, QRS duration, QT duration, QTc Bazett, QTc Fridericia, QTc manual) summary statistics will be presented at each scheduled assessment for actual values and changes from baseline.

For interpretation of clinical significance (within normal limits / abnormal, not clinically significant / abnormal, clinically significant / not evaluable), a frequency table will be presented at each post-dose assessment as well as the changes from baseline with the following categories: improved, stable, worsened, clinically significant worsening.

3.2.2.5 *Physical examination*

Physical examination (normal, abnormal, specification for abnormal result) will be listed by subject number and visit. Any unscheduled physical examination will be flagged [U] in the listings.

3.2.3 *Missing data and outliers*

3.2.3.1 *Missing data*

- Efficacy endpoints

No imputations will be made for missing data.

- Safety endpoints

If a value requires a retest (for laboratory values, vital signs, ECG), the closest non-missing reliable value to the scheduled visit is used in the summary tables. An assessment is considered reliable if it is performed without any technical problem or altered blood samples and if the result is within the range of plausible values.

Any repeat or additional assessments performed will be included in the individual subject data listings.

For AEs with missing information for the intensity and/or causality, the value will not be replaced and will be summarised as a separate category.

For all other variables, no imputations will be made for missing data.

3.2.3.2 *Missing or incomplete dates*

In all listings, missing or incomplete dates should be left as they have been recorded. However, for calculation / sorting / assignation based on dates, the following methods will be used:

- The most conservative approach will be systematically considered (i.e., if the onset date of an AE/concomitant medication is missing / incomplete, it is assumed to have occurred during the study IIP phase (i.e. a TEAE for AEs) except if the partial onset date or other data [stop date, ...] indicates differently).
- A missing/incomplete date of medical history or disease diagnosis will be assumed to have occurred before IIP administration.
- If a partial date and the associated information do not allow to state about the assignation to a group / category, all the possible groups / categories will be considered (i.e.: an AE could be assigned to several possible doses at event onset according to its partial onset date and stop date. Particularly an AE with missing start date will be assigned to each dose received before its end date. Similarly, a medication with partial start and stop dates could be considered as prior and concomitant treatment).
- Where possible, the derivations based on a partial date will be presented as superior inequalities (i.e., for an AE started in FEB2004 after the administration performed on 31JAN2004, the days since last administration will be " ≥ 2 ". Similarly, the duration of ongoing AEs or medication will be " $\geq xx$ " according to the start and last visit dates).

3.2.3.3 *Outliers*

Any outlier identified prior to database lock which is impossible/implausible will be excluded from the analysis. For other identified outliers, the impact should be assessed by performing the statistical analysis with the actual values and at least one other analysis eliminating or reducing the outlier effect.

If any outliers are identified after database lock the statistical analysis should be performed with the actual values and at least one other analysis eliminating or reducing the outlier effect.

A search of outliers should be performed before the database lock and actions with the sponsor should be defined (e.g. edition of queries).

3.2.4 *Subject disposition*

The numbers and percentages of subjects included in each of the Eligibility screened, Safety, ⁶⁸Ga-OPS202 screened, sstr2 positive and sstr2 positive evaluable population will be tabulated. The reasons for subject exclusions from each of the populations will also be tabulated.

A listing of dates and time of assessments (relative day) will be presented by subject.

A summary table will be presented on Safety population presenting the number of subjects at each visit and identifying the number of subjects who withdrew from the study over time. A unique flow chart will be drawn with the number of subjects in each population.

The listing of subject disposition will include the subject exposure in the study. The definition of the study exposure is defined in the Appendix 1 Derived data.

3.2.5 *Withdrawals*

Discontinued subjects will be listed and a summary table of the number and percentage of subjects who completed and withdrew from the study and the reasons for withdrawal will be presented.

3.2.6 *Demographic and baseline characteristics*

In order to characterise the subjects, descriptive summary statistics (n, mean, SD, median, minimum, and maximum) or frequency counts of demographic and baseline data will be presented for the Safety population.

Summary statistics will be provided for demographic and baseline characteristics:

- race/ethnicity, age and age class
- height, weight at screening, body mass index (BMI) and BMI in categories at screening (refer to Appendix 1, Derived data)
- Eastern Cooperative Oncology Group (ECOG) performance status

Summary statistics of the tumour characteristics will be provided:

- Tumour, node and metastasis (TNM) staging
- presence of metastases
- location of metastases
- Estrogen Receptor status
- Progesterone Receptor status
- IHC result
- ISH result

All demographic and baseline characteristics will be listed by subject.

Pregnancy tests performed will be listed by subject, and by visit.

3.2.7 *Medical and surgical history*

Medical and surgical history will be coded using MedDRA Version 19.1 or higher.

Listings will present the preferred term and verbatim text. The listings will be sorted by subject number, date of diagnosis, primary SOC, PT and verbatim text.

A frequency table of the number and percentage of subjects will be provided for all medical and surgical history by primary SOC and PT on the safety population.

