1.3.2 Subjects assessments

1.3.2.1 Efficacy assessments

For the primary, secondary and exploratory endpoints all the sets of images of the three time points obtained at Visit 2, one ceCT and one ^{18}F -FDG-PET will be sent to an ICL for quality control and management of the reads.

The centralised reads will be undertaken by two independent experienced radiologists and/or nuclear medicine physicians, and a third for adjudication of discordances for most of the reads. The readers will be specifically trained for this protocol.

All the images will be reviewed according to the workflow illustrated in [Figure 2](#) and [Figure 3](#) below.

Figure 2 Flow Chart of the Independent Review Methodology (68Ga-OPS202)

[figure not shown]
[figure not shown]

Figure 3 Flow Chart of the Independent Review Methodology (18F-FDG-PET standard-of-truth)

Full details of the read design and conduct are provided in the Independent Review Charter (IRC).

For the primary endpoint analysis, the number of lesions and quality of the images will be taken into consideration by the readers. Scans will be blinded to subject identification, site and timing post injection. In case of discrepancy in lesion counts, images will go to the adjudicator (third reader) for a final read and adjudication.

For image quality, the readers will compare the three ^{68}Ga -OPS202 PET/CT scans contemporaneously for each subject and note which image(s), if any, provides superior images based on overall image quality and lesion count.

Details for computation and analysis of primary efficacy criterion are provided in section 3.2.1.1.

The sequence of image display and recording of results will be as follows on a per subject basis:

- (1) Review of the three image sets of ^{68}Ga -OPS202 scans in randomised fashion with CT image fusion. The ceCT images acquired will be used for co-registration. Two readers will read and a third will adjudicate any differences.
- (2) ^{18}F -FDG-PET images for standard-of-truth assessments will be reviewed by two radiologists not involved in ^{68}Ga -OPS202 PET/CT images read, and the lesions mapped to the ^{68}Ga -OPS202 read. Two readers will read and a third will adjudicate any differences.
- (3) SUV_{max} and SUV_{mean} calculations of the five most avid lesions per organ on ^{68}Ga -OPS202 PET scans (primary breast lesion, liver, lymph nodes, bone, lungs and brain) will be conducted by the ICL after identification of the lesions by one of the primary readers.

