2.3 Primary population

The co-primary analysis based on the primary efficacy endpoint to determine sstr2 positive percentage will use the ^{68}Ga -OPS202 screened population as the denominator. The co-primary analysis based on the primary efficacy endpoint to assess optimum imaging timing of the PET scan following ^{68}Ga -OPS202 injection will be performed on the sstr2 positive evaluable population.

In addition, as a supportive post-hoc analysis, the sstr2 positive prevalence may also be evaluated on the agreed optimum timepoint population.

All secondary and exploratory efficacy endpoints will be evaluated on the sstr2 positive evaluable population.

The assessment of safety and tolerability will be based on the safety population.

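### The relative lesion count lists an exact value (100% when both scans show 35 or more lesions) where the SAP itself says the counts cannot be made accurately

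*SAP*

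**What the plan says.** The definition in SAP 3.2.1.2 c) begins: "The relative lesion count is the ratio of the number of lesions detected by" OPS202 at each of the three acquisition times, "compared to the number of lesions assessed by standard-of-truth", which is the FDG scan. Protocol 3.2.2.2, 7(b) and 11.4.4 have the same ratio and label it descriptive.

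On level, the SAP says: "Relative lesion count will be computed over all lesions of all organs and for each of the following organs".

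The ceiling rule appears only in the SAP and has two parts:
- Both scans high: "If there are 35 lesions or more counted on both" scans, "then the relative lesion count will be set to 100" per cent.
- One scan high: "the relative lesion count will be computed using a count of 35 lesions for the scan showing more than 35 lesions".

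Item a) of the same section gives the reason for a ceiling. At 35 or more lesions in any one organ, counting is not feasible because it cannot be done accurately, and the result is shown as a category.

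On matching, SAP 1.3.2.1 step (2) has separate readers assess the FDG scans: "PET/CT images read, and the lesions mapped to the" OPS202 read. The ratio does not use that mapping. Lesion-based sensitivity against FDG (item f) and the OPS202/FDG lesion-count correlation (item i) are both marked as not provided.

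The opening of 3.2.1.2 says that selection of the optimal imaging time will draw on the outputs for all secondary and exploratory endpoints. For the relative lesion count, that output is an individual listing by subject, organ and timepoint.

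**The concern.** A count of 35 or more is a censored value: it is known to be at least 35 and nothing else. Item a) treats it that way and item c) does not. Two censored counts become a precise 100%, and one censored count becomes a precise ratio with 35 plugged in. A reader of the listing cannot tell a measured 100% from an assigned one by looking at the ratio.

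The endpoint exists to compare three acquisition times. A subject whose OPS202 count is capped at two or more of them shows the same ratio at each, which looks like a finding of no difference when it is an absence of information.

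A second, lesser matter applies at any count. The ratio divides totals, so a lesion seen only on OPS202 offsets one seen only on FDG. Because FDG is called the standard-of-truth and both of the other FDG comparisons were dropped, this ratio is the only FDG comparison for which the SAP still specifies an output. It is likely to be taken for detection performance.

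**Working it through.** **Inputs.** The ratio, the ceiling of 35 and the two ceiling rules come from SAP 3.2.1.2 c). The statement that counts of 35 or more in an organ are not accurate comes from 3.2.1.2 a). The documents report no lesion counts, so every count below is an illustrative assumption. Figures above 35 stand for a possible true state, not for something the core laboratory would record.

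**Rule as written**, with G = OPS202 count and F = FDG count:
- G ≥ 35 and F ≥ 35: ratio = 100%
- otherwise: min(G, 35) / min(F, 35)

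**1. The plan's own figure.** With both capped, 35/35 = 100%. The stated value is reproduced; it amounts to assuming that the two unknown counts are equal.

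**2. Both capped: the ratio is unknown.**

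| True G | True F | G/F | Listed |
|---|---|---|---|
| 36 | 90 | 40% | 100% |
| 36 | 120 | 30% | 100% |
| 120 | 36 | 333% | 100% |

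**3. One capped: only a bound is known.**
- G = 20, F ≥ 35: the ratio is at most 20/35 = 57%. The SAP lists 57%. If F were 80, the ratio would be 20/80 = 25%.
- G ≥ 35, F = 20: the ratio is at least 35/20 = 175%. The SAP lists 175%. If G were 80, it would be 80/20 = 400%.

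**4. Across timepoints.** Each subject has one FDG scan, so F is fixed. Take G = 40, 60 and 90 at the three times:
- F = 50: listed 100%, 100%, 100%; underlying 80%, 120%, 180%.
- F = 20: listed 175%, 175%, 175%; underlying 200%, 300%, 450%.

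If only F is capped and G stays below 35, the listed ratio still moves with G and the ordering of timepoints is kept. Masking therefore needs G ≥ 35 at two or more timepoints.

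**5. The all-organ ratio.** The ceiling in a) is per organ; c) does not say how it applies to the all-organ total.
- OPS202 nodes 20 + bone 16 = 36; FDG nodes 34 + bone 34 = 68. Every organ is countable and 36/68 = 53%. Read literally, both totals reach 35 and 100% is listed.
- OPS202 nodes 10 + bone 20 = 30; FDG nodes 10 + bone 35 or more, hence at least 45. The ratio is at most 30/45 = 67%. Capping the FDG total at 35 lists 30/35 = 86%, above the largest value possible.

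**6. Unmatched totals, no ceiling involved.** With G = 4 and F = 4 the listed ratio is 4/4 = 100% for 0, 1, 2, 3 or 4 matched lesions; the matched share of FDG lesions would be 0%, 25%, 50%, 75% or 100%. Organ-level listing helps only between organs: nodes 4 against 2 and bone 0 against 2 give 200% and 0%, while the all-organ ratio is 4/4 = 100%. Mismatch inside one organ stays invisible.

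**The case against.** The best defence is that this is a relative count and is named as one. The protocol defines it by this formula, it can exceed 100%, and nothing in the SAP calls it agreement or sensitivity. Changing the numerator to matched lesions would in substance turn it into the lesion-based sensitivity that the protocol lists separately and the SAP dropped after early termination. That stands, and the protocol-defined ratio should be kept.

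It can also be said that the timing information is lost when lesions cannot be counted, not when the ratio is formed, and that OPS202 counts are listed by subject, organ and timepoint, so a capped OPS202 count can be recognised. This is partly right: no rule for the ratio can recover the missing counts. But the rule reports a number where none is known. Recognising a capped ratio also needs the FDG count, and the body of the SAP mentions no listing of FDG counts (the templates in Appendix 2 are not available).

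Three stronger readings are tempting and are not supported:
- **That any high count forces 100%.** It is forced only when both scans reach 35.
- **That restricting the endpoint to OPS202-positive women inflates it.** SAP 2.3 does say: "All secondary and exploratory efficacy endpoints will be evaluated on the sstr2 positive evaluable population". But the timing objective concerns women with sstr2 positive disease, and OPS202-negative women carry no information on timing. The share of positive women is already the first co-primary endpoint.
- **That a mean ratio over all scanned women would be far lower.** No mean is planned; only individual values are listed.

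**Conclusion.** The ceiling rule is wrong as written. It lists an unknown ratio as exactly 100% when both scans show 35 or more lesions, and lists a bound as a value when one does, against the SAP's own statement about such counts. In the illustrations, 100% stands for anything from 30% to 333%, and 57% stands for 57% or less. Where OPS202 is capped at two or more timepoints, the endpoint shows no difference whatever the truth. The unstated handling of the all-organ total adds a further, avoidable error.

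The unmatched numerator is not an error against the protocol. A reader might infer that 100% means every FDG lesion was found; the formula does not support that, and the SAP should say so.

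The practical size is small. This is an other secondary endpoint, descriptive and listed only, in a study stopped early with limited data. The population is newly diagnosed, and completion required only two advanced cases among 16, so counts of 35 or more on both scans may be rare; the documents do not say. The point is still worth correcting because the listing feeds the choice of imaging time.

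**What to change.** In SAP 3.2.1.2 c):

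1. **Both counts 35 or more in an organ:** list the ratio as not estimable.
2. **One count 35 or more:** list a bound. If FDG is capped, give an upper bound (at most G/35); if OPS202 is capped, a lower bound (at least 35/F). This fits SAP 3.2.11, which already lists values beyond a detection limit as such.
3. **All-organ ratio:** apply the ceiling per organ only. A total of 35 or more made up of countable organs is used as it is. A capped organ contributes at least 35, so the all-organ ratio becomes a bound if only one scan has a capped organ, and not estimable if both do.
4. **Interpretation:** keep the protocol's ratio and add a sentence saying that it is a relative count of unmatched totals, not detection performance.
5. **If the core laboratory exports the lesion map:** list matched, OPS202-only and FDG-only lesions by organ and timepoint beside the ratio. Whether it does depends on the Imaging Review Charter, which is not among the documents, so this should be confirmed first.

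Items 1 to 4 cost SAP wording and listing programming, with no new imaging or reads. Item 5 needs one more listing and possibly a further data transfer. Some entries will show a bound or text where a number stood.
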